PART B STUDY DESCRIPTION

TITLE OF PROTOCOL	Seizure-like Hippocampal Activity in Alzheimer's Disease Neurodegeneration		
Principal Investigator	[name].		
Co-Investigators	[name]; [name]; [name]		
Mailing Address	[name]		
E-Mail Address	[contact]		
P.I.'s Telephone	[name]	P.I.'s Pager [name]	Fax: [name]
Sponsor/Funding Source	Fidelity Biosciences Research Initiative; Neurology Department internal funding		

B1. PURPOSE OF PROTOCOL

To test the hypothesis that increased hippocampal perfusion on arterial spin labeling MRI in patients with Alzheimer's Disease (AD) is partially driven by focal epileptiform activity, and that this abnormal activity contributes to memory dysfunction.

Here we propose applying an imaging technique, arterial spin labeling MRI (ASL-MRI), ideally suited for testing this hypothesis. We will utilize a pharmacological probe, levetiracetam, to test whether sub-clinical epileptiform activity is driving increases in hippocampal perfusion and contributing to the declarative memory impairment in AD. Levetiracetam is an antiepileptic drug (AED) that inhibits epileptiform activity. Levetiracetam inhibits burst firing without affecting normal neuronal excitability. We will study patients with mild AD in three sessions, counterbalanced for order, in a crossover design. In each session, participants will undergo a baseline electroencephalogram (EEG). They will then be given either a placebo or intravenous levetiracetam low dose (2.5 mg/kg) or high dose (7.5 mg/kg). After drug administration, repeat EEG, ASL-MRI perfusion imaging, and behavioral testing will be conducted. Participants will return at 1-2 week intervals for the second and third sessions in the other conditions (levetiracetam low dose / levetiracetam high dose / placebo). This study will test whether increased hippocampal perfusion in AD is caused by epileptiform activity, whether this activity is contributing to memory impairment, and whether antiepileptic medications might be a new avenue of treatment in AD. If validated, ASL-MRI would be an ideal tool to non-invasively determine whether antiepileptic medications are effective in decreasing aberrant excitatory activity in the hippocampus in AD.

Aim 1: To determine whether increased hippocampal perfusion in AD is caused by epileptiform activity.

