Hypothesis 1: Hippocampal perfusion in AD will be decreased after the administration of an antiepileptic medication, levetiracetam, but not after placebo.

Aim 2: To determine whether inhibition of burst firing can improve cognitive performance and neural function in cortical regions beyond the hippocampus.

Hypothesis 1: Decreases in hippocampal perfusion will correlate with improvements in

measures of declarative memory and spatial memory.

Hypothesis 2: Decreases in hippocampal perfusion will correlate with increases in cortical perfusion, particularly in lateral temporal and parietal association cortices.

B2. SIGNIFICANCE AND BACKGROUND FOR THE STUDY

Seizures and Alzheimer's Disease

Alzheimer's disease (AD) is associated with an increased risk of unprovoked seizures and accounts for approximately 2% of all epilepsy¹. Clinical seizures develop in 1.5 -17% of long-term AD survivors, most commonly in those with early age at disease onset and with familial AD²⁻⁴. In familial AD due to mutations in presenilin, epilepsy is much more prevalent, approaching 80% of affected members⁵⁻⁷. Seizures may be more common in sporadic AD, however, than previously reported⁸. Seizures may be under-recognized in patients with dementia. Subjective seizure auras such as *déjà vu*, olfactory hallucinations, and other auras are uncommon in AD³. Clinical manifestations of temporal lobe seizures are often subtle. For example, focal seizures restricted to the hippocampus may produce only mild confusion or amnesia without other outward signs⁹. Fluctuations in memory or wandering in AD can be due to unrecognized complex partial seizures¹⁰. Such seizures might easily be missed in patients with baseline memory and cognitive deficits. Seizures in AD are usually considered to be rare and late byproducts of a diffuse neurodegenerative process, but recent evidence from animal studies has raised the intriguing possibility that epilepsy plays a more central role in the pathophysiology of AD.

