In our previous study of 22 AD participants (mean age=75.6, MMSE 22.2) and 16 demographically matched controls (mean age=72.6, MMSE 27.9), we measured hippocampal, amygdala, and parahippocampus CBF as a % of visual cortex. In addition, we corrected for atrophy on a voxel-by-voxel basis by measuring gray matter volume in each voxel using T1 maps that were acquired in the same sequence as the perfusion maps. A region of interest analysis was performed using an *a priori* template, with left and right regions averaged together. The table below shows the results of the atrophy-corrected perfusion measurements as a percentage of visual cortex perfusion.

	Hippocampus	Amygdala	Parahippocampus
Mean AD (SD)	0.96 (0.29)	0.61 (0.19)	0.74 (0.20)

Mean CN (SD)	0.77 (0.17)	0.52 (0.11)	0.62 (0.14)
Prob of difference	0.008	0.043	0.017

Choice of levetiracetam as a pharmacologic probe

In this pilot study, we aim to determine whether the hippocampal hyperperfusion seen on ASL-MRI reflects abnormal epileptiform activity by using levetiracetam as a pharmacological probe. Even intermittent epileptic discharges, in the absence of clinically obvious seizures, may lead to memory impairment. If so, a reduction of hippocampal epileptiform activity could improve declarative memory and potentially alter progression of AD.

Levetiracetam, a newer antiepileptic drug, decreases the frequency and limits propagation of epileptiform activity without affecting normal neuronal excitability^{28, 29}. The mechanism of action of levetiracetam is not fully understood, but it binds specifically to synaptic vesicle protein SV2A and likely modulates its function³⁰. Levetiracetam may also have an indirect effect on GABA-A inhibitory neurotransmission and on high-voltage activated calcium channels. Levetiracetam decreases cortical excitability measured by transcranial magnetic stimulation³¹. In a study of levetiracetam in photosensitive epilepsy, 250mg oral doses decreased epileptiform activity induced by photic stimulation within 1 hour, and 750mg oral doses completely abolished epileptiform activity³². Acute dosing of levetiracetam 500mg caused significant reduction in the frequency of interictal epileptiform activity in 8/10 patients with epilepsy³³. Because of its rapid onset of action and effect on interictal epileptiform activity as well as seizures, levetiracetam is an excellent candidate AED to examine changes in perfusion on ASL-MRI.

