Twenty subjects with mild AD (MMSE≥20) will participate in this study in the Clinical Research Center at Beth Israel Deaconess Medical Center. Subjects will be screened to ensure they meet inclusion and exclusion criteria and will provide written informed consent before any study procedures are performed. Each eligible subject will undergo three sessions, held 1-2 weeks apart, in a double blind, within-subject crossover design, counterbalanced for order (placebo / levetiracetam 2.5 mg/kg / levetiracetam 7.5 mg/kg), Figure 3. During each session, placebo or levetiracetam will be administered intravenously over 20 minutes. Drug administration will occur during EEG recording so that neurophysiological recordings can be acquired before, during, and after administration. Changes in EEG background frequency and level of synchrony will be analyzed⁴⁴⁻⁴⁶. After drug administration and EEG recording, hippocampal perfusion and functional connectivity will be measured with ASL-MRI and resting BOLD fMRI. Finally, participants will undergo a cognitive battery with memory tests particularly sensitive to hippocampal function (declarative memory, attention, working memory and executive function).

[figure not shown]

Figure 3. Overall paradigm. Participants will undergo testing in 3 sessions counterbalanced for order, with placebo, low dose LEV or higher dose LEV. Drug will be administered intravenously during EEG recording. Imaging will be acquired with anatomical, perfusion and resting state bold MRI. Cognitive testing will be performed with a battery including a memory test particularly sensitive to hippocampal function as well as other tests of frontal function.

2. Study Rationale

This protocol has three primary goals: to test the hypothesis that increased hippocampal perfusion in AD is at least partially driven by epileptic activity, that lowering epileptic activity may improve cognitive performance, and that perfusion MRI can be used as a non-invasive assay of the effects of medications that decrease epileptic activity in AD.

3. Subject Recruitment and Screening

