We plan to study 20-25 subjects at BIDMC. We anticipate screening 25 subjects to enroll and randomize 20 eligible subjects. We have performed a power calculation based on our previous study finding hyperperfusion of the hippocampus in AD as compared to controls ²³. With a sample size of 20 AD participants, we will have a 72% probability of detecting a decrease in perfusion after levetiracetam, assuming administration of the drug lowers hippocampal CBF only to normal levels. This estimate is likely overly conservative for two reasons. First, the within subject design should markedly decrease variance. Second, if epileptiform discharges are contributing to hippocampal hyperperfusion and damage, then briefly ceasing the abnormal activity with drug should reveal underlying hypoperfusion like that typically seen in temporal lobe epilepsy.

Data Analysis:

The primary study outcomes are:

- Differences in hippocampal perfusion on ASL-MRI
- Differences in memory performance

The secondary study outcomes are:

Differences in whole brain regional cerebral blood flow on ASL-MRI
Differences in working memory and executive functions
Differences in EEG measures (alpha peak power, beta band power, delta/theta band power, coherence)

Behavioral Data

Measures of memory encoding, retrieval and storage will be analyzed using repeated measures ANOVA. We will test our a priori main hypothesis of improved memory performance after drug. In a secondary analysis, we will measure effects of drug on working memory and executive functions in a similar manner.

Imaging Data

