We will do two analyses, one focused specifically on hippocampal perfusion and a second analyzing regional CBF throughout the whole brain. First, we will use a repeated measures ANOVA with hippocampal perfusion and session (placebo, 2.5mg/kg and 7.5mg/kg) being the factors. Hippocampal perfusion is measured as a percentage of visual cortex perfusion, using a template available within the Statistical Parametric Mapping package. Second, we will measure regional CBF throughout the whole brain using SPM5 and measure changes after drug vs. placebo using a random effects model and accounting for the repeated measures design. In addition to direct analysis of perfusion, we will examine cortical changes in CBF correlated with our seed region in the hippocampus. We predict that decreases in perfusion in the hippocampus after levetiracetam will correlate with increases in perfusion in association cortical regions. Lastly, we will test for correlations between behavioral measures of memory and regional changes in CBF in hippocampus and whole brain. We predict that decreases in hippocampal perfusion will paradoxically correlate with improved declarative memory performance.

EEG Data

EEG will be visually analyzed for presence of epileptiform activity. Peak alpha power, beta band power, delta/theta power, and coherence will be calculated using BESA (Brain Electrical Source Imaging) software and Persyst MagicMarker software. Measures will be analyzed using repeated measures ANOVA. We hypothesize that levetiracetam will decrease source coherence in temporal regions.

Analyses will be performed in the Cognitive Neurology Unit, Magnetic Resonance Imaging Center of the Department of Radiology, and EEG Laboratory at Beth Israel Deaconess Medical Center.

C. Subject Selection

Subjects will be recruited from the Cognitive Neurology Unit at BIDMC. The P.I., who specializes in neurodegenerative disorders, maintains an active clinic and treats over 100 patients with AD. In addition, the Cognitive Neurology Unit has over 13,000 patient visits per year.

Inclusion Criteria:

- Meets the NINCDS-ADRDA criteria for probable Alzheimer's disease
- Mild AD (MMSE \geq 20)
- Age \geq 50 years
- English as first language

Exclusion Criteria:

- A history of seizures prior to the onset of AD
- Familial Alzheimer's Disease due to known genetic mutations
- Current use of an anti-epileptic medication

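### Does the 72% power figure mislead because it ignores the within-subject design and covers only full normalisation of hippocampal perfusion?

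*Combined protocol and SAP*

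**What the plan says.** The Sample Size Justification bases its calculation on the earlier comparison of AD patients with controls and reports, for 20 AD participants, a "72% probability of detecting a decrease in perfusion after levetiracetam, assuming administration of the drug lowers hippocampal CBF only to normal levels". It continues: "This estimate is likely overly conservative for two reasons". The first reason reads "First, the within subject design should markedly decrease variance". The second is that suppressing the discharges may uncover hypoperfusion below the normal level. No test, alpha, sidedness, contrast, within-subject correlation or SD of differences is stated.

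The planning data are in B2 ("In our previous study of 22 AD participants" and 16 controls): hippocampal perfusion relative to visual cortex was 0.96 (SD 0.29) in AD and 0.77 (SD 0.17) in controls.

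For the analysis, Imaging Data says "we will use a repeated measures ANOVA with hippocampal perfusion and session", the sessions being placebo and the two doses. Aim 1, Hypothesis 1 is that hippocampal perfusion "will be decreased after the administration of an antiepileptic medication, levetiracetam, but not after placebo". B1 says the raised perfusion "is partially driven by focal epileptiform activity", and the Study Rationale says it "is at least partially driven by epileptic activity".

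**The concern.** Two things look wrong. First, the power figure appears to belong to a different design: two independent groups, rather than one group measured three times. Second, the only effect considered is removal of the whole excess, and this is presented as the cautious case. If epileptiform activity causes only part of the excess, suppressing it need not bring perfusion back to normal, so the effect closest to the stated hypothesis has no power figure.

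The 72% is the only quantitative support for 20 participants, and readers are told that it is probably too low. If the true effect were half the excess and the within-subject correlation moderate, the trial would miss it more often than not. A null result could then be taken as evidence against the partial contribution that the trial sets out to examine.

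**Working it through.** **Inputs.** From B2: means 0.96 and 0.77, SDs 0.29 and 0.17. From the Sample Size Justification: n = 20. Assumed, because the documents do not give them: alpha 0.05 two-sided, the within-subject correlation rho, and the same SD at each session (0.29, or the root-mean-square value below).

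**1. Reproducing 72%.**
- Difference: 0.96 − 0.77 = 0.19.
- Root-mean-square SD: √[(0.29² + 0.17²)/2] = √[(0.0841 + 0.0289)/2] = √0.0565 = 0.238.
- Two groups of 20, normal approximation: 0.19 / (0.238 × √(2/20)) = 2.53, and power = Φ(2.53 − 1.96) = 71.5%.

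A two-sample t-test with SD 0.23 gives 72.1%. The 71.5% also results from a paired calculation with rho = 0 and SDs 0.29 and 0.17, because the variance of the difference is then the same (0.0841 + 0.0289 = 0.1130). The exact test cannot be identified, but these routes use no within-subject correlation, as the paragraph itself implies.

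**2. Power of the crossover contrast, one dose versus placebo.** Paired t-test, 19 degrees of freedom, noncentral t, SD of differences = SD × √[2(1 − rho)]. At rho = 0.5 this equals the session SD, so the standardised effect for the full excess is 0.19/0.29 = 0.66 or 0.19/0.238 = 0.80. Each range runs from SD 0.29 to SD 0.238.

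| Share of the 0.19 removed | rho 0.3 | rho 0.5 | rho 0.7 | rho 0.8 |
|---|---|---|---|---|
| 100% | 65-82% | 79-92% | 95-99% | 99% or more |
| 75% | 42-58% | 55-72% | 77-91% | 91-98% |
| 50% | 22-30% | 29-40% | 44-59% | 59-77% |

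At rho 0.9, half the excess gives 87-97% with equal session SDs, or 73% if the SDs are 0.29 and 0.17.

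**3. Correlation at which the crossover reaches 72%.** With n = 20, 72% power needs a standardised paired effect of 0.599.
- Full excess: SD of differences at most 0.19/0.599 = 0.317. Then rho = 1 − 0.317²/(2 × SD²) = 0.40 for SD 0.29 and 0.11 for SD 0.238. With SDs 0.29 and 0.17 it is 0.13.
- Half the excess: SD of differences at most 0.095/0.599 = 0.159, so rho = 0.85, 0.78 and 0.89 for the same three cases.

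**4. Other choices of test, half the excess.**
- One-sided 0.05: 41-53% at rho 0.5 and 57-72% at rho 0.7.
- Both doses averaged against placebo, same effect at each (SD of differences = SD × √[1.5(1 − rho)]): 36-50% and 55-71%.
- Omnibus three-session ANOVA, same effect at each dose: 29-41% and 45-62%.

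**The case for a change.** The strongest case for a change is that the conservatism remark may lead a reader to think power exceeds 72% for whatever effect the drug has. Halving the effect can outweigh the gain from pairing, and neither a one-sided test nor averaging the doses removes the shortfall at moderate correlation. Hippocampal perfusion is a primary outcome, and the repair would cost one paragraph and a small table.

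The arithmetic stands, and so does the observation that the assumptions are unstated. The inference that the plan is wrong does not, for three reasons:

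- The remark is hedged, and it refers to an estimate whose condition, return to normal perfusion, is stated in the sentence before it. The plan makes no power claim for a smaller effect.
- Full normalisation is not an arbitrary planning value. B2 reports that two weeks of oral levetiracetam normalised hippocampal hyperperfusion in mild cognitive impairment. The population, regimen and MRI method (BOLD) differ, so the support is limited. The Study Rationale's wording also allows a full effect. No document gives 50% or 75%.
- A blanket warning that partial effects need a high correlation would overstate the case. Removal of 75% already gives 72% power at rho 0.5 with SD 0.238, and 77-91% at rho 0.7.

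The plan's second reason, hypoperfusion below normal, is not quantified and carries little weight in either direction.

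**Conclusion.** No change is needed. The 72% reproduces (71.5% by normal approximation), its condition is stated, and the paragraph itself says that the within-subject gain is left out. For the scenario it describes, that omission understates power once rho exceeds about 0.1 to 0.4; at rho 0.5 the crossover has 79-92%. For half the excess, power could be as low as 29-40% at rho 0.5 or as high as 87-97% at rho 0.9. That range depends on a correlation and a fraction removed that the documents do not supply, as well as on two-sided 0.05 and equal session SDs of 0.238 to 0.29.

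What remains is missing detail in a pilot's sample-size paragraph. A sensitivity table built on assumed correlations would leave the 20 participants, the repeated measures analysis and the results as they are. When the trial reports, the observed SD of the within-subject differences and the confidence interval for the change will show how large an effect a null result can exclude, and will do so better than any planning figure. An author who wished to could add the assumptions behind the 72% and note that the conservatism refers to full normalisation; this is optional.

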Participants will undergo declarative memory testing with the Free and Cued Selective Reminding Test, a task that is particularly sensitive to hippocampal function ⁴⁸. In addition, a short battery will be administered to test executive function, naming, visuospatial ability and semantic function (Trail Making Test Parts A+B, Phonemic fluency Test, Boston Naming Test 15-item version, clock drawing, category fluency). The primary endpoint for memory testing will be the free recall score from the Free and Cued Selective Reminding Test. This battery is fairly brief (30 min) but sensitive to both hippocampal function and changes in other cognitive realms impaired in AD.

p. Adverse events observed by investigator or reported spontaneously by the subject

6. Study Plan

The following assessments and procedures will be done at each study visit:

a. Screening visit

1. Informed consent
2. Demographics and baseline characteristics
3. Medical history
4. Neurologic history
5. Recent and concomitant medications
6. Blood collection for blood urea nitrogen and creatinine)
7. Vital signs: Systolic and diastolic blood pressure, heart rate, and respiratory rate; weight
8. Physical exam
9. Neurological exam
10. Mini-Mental Status Examination

b. Visits #1-3 (identical procedures, visit length 5-7 hours)

1. Vital signs: Systolic and diastolic blood pressure, heart rate, and respiratory rate; weight
2. Physical exam
3. Neurological exam
4. IV catheter placement
5. EEG (60 minute recording)
6. Study drug infusion (20 minutes)
7. Vital signs at 10, 20, 30 minutes after infusion
8. Imaging paradigm (60 minutes)
9. Behavioral testing (60-90 minutes)
10. Adverse events

There will be scheduled breaks between tests and scheduled lunch

c. Telephone follow-up

1. Follow up for adverse effects

B. Statistical Considerations

Sample Size Justification:

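### Must the analysis section restate free recall as the primary memory score and add a success rule for its two primary outcomes?

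*Combined protocol and SAP*

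**What the plan says.** The plan is one combined protocol and SAP.

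- **Section B3.A.5.o, Behavioral testing:** "The primary endpoint for memory testing will be the free recall score from the Free and Cued Selective Reminding Test".
- **Section B3.B, Data Analysis:** two primary outcomes are listed, hippocampal perfusion on ASL-MRI and "Differences in memory performance". No test or score is named for the second.
- **Section B3.B, Behavioral Data:** "Measures of memory encoding, retrieval and storage will be analyzed using repeated measures ANOVA", followed by "We will test our a priori main hypothesis of improved memory performance after drug".
- **Section B3.B, Imaging Data:** "we will use a repeated measures ANOVA with hippocampal perfusion and session (placebo, 2.5mg/kg and 7.5mg/kg) being the factors".
- **Section B3.B, Sample Size Justification:** the only power statement concerns perfusion, "we will have a 72% probability of detecting a decrease in perfusion after levetiracetam". The investigators call it conservative, partly because "the within subject design should markedly decrease variance".
- **Section B1:** Aim 1 concerns perfusion ("Hippocampal perfusion in AD will be decreased after the administration of an antiepileptic medication, levetiracetam, but not after placebo"). Aim 2 concerns cognition and cortical function.

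No section gives a significance level, a test order, an alpha split, or a statement that one or both primary outcomes must be positive. The Study Overview calls the trial a pilot.

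**The concern.** Two things look wrong.

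First, someone reading only the statistical section sees several memory constructs and a main hypothesis about memory, with no score attached. If the choice were really open, the most favourable selective-reminding measure could be presented afterwards as the main memory result.

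Second, with two primary outcomes and no rule for combining them, the reader cannot tell what a positive study is. If either outcome is enough and each is tested at 0.05, the false-positive rate is nearly twice that of one test. If encoding, retrieval and storage were also each treated as primary beside perfusion, there would be four tests and the rate would be higher still.

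At stake are the credibility of a memory claim and the overall error rate of the primary analysis.

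**Working it through.** **1. The plan's own figure.** Inputs from the hippocampus column of the table in section B2: AD 0.96 (SD 0.29), controls 0.77 (SD 0.17).

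- Difference: 0.96 − 0.77 = 0.19.
- SD: √((0.29² + 0.17²)/2) = √0.0565 = 0.238.
- Treated as two independent groups of 20: 0.19/(0.238 × √(2/20)) = 2.53. Power at two-sided 0.05 is Φ(2.53 − 1.96) = 71.5%.

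This matches the stated 72%. The figure is therefore an unadjusted test of perfusion alone, and 0.05 is inferred from the match because no level is stated.

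**2. Is the memory score open?** The Behavioral testing section assigns primary status to one score. The Data Analysis section names the domain, and Behavioral Data names the family of measures to be analysed. These fit together: the family is analysed and free recall leads it. Four primary tests would give 1 − 0.95⁴ = 18.5% if independent, but promoting three memory measures would depart from the document's own primary memory endpoint.

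**3. Error rate with two primary outcomes.** Independent tests: 1 − 0.95² = 9.75%. Simulation used 20 subjects, three sessions, no true effect and the session F test on 2 and 38 degrees of freedom at 0.05:

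| Perfusion–memory correlation (assumed) | Either, any direction | Either, predicted direction | Both significant |
|---|---|---|---|
| 0 | 9.8% | 5.0% | 0.2–0.3% |
| −0.5 | 9.2% | 4.6% | 0.8% |
| −0.7 | 8.5% | 4.3% | 1.5% |

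One test alone gives 5% in any direction and 2.5% in the predicted direction. Inflation appears only in the two either-counts columns.

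**4. What a formal rule would cost.** For the session F test, assume that both doses bring perfusion to the control mean. Noncentrality = 20 × (2/3) × 0.19²/(SD² × (1 − r)), where r is the within-subject correlation. The documents do not give r, so it is shown as a range.

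| r | Power at 0.05, SD 0.238 | Power at 0.025, SD 0.238 | Power at 0.05, SD 0.29 |
|---|---|---|---|
| 0 | 71% | 60% | 53% |
| 0.3 | 86% | 78% | 69% |
| 0.5 | 95% | 91% | 84% |
| 0.7 | 99.7% | 99.4% | 97% |

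- *Fixed order, perfusion first:* memory becomes exploratory whenever perfusion fails. That is 29%, 14%, 5% and under 1% of trials with SD 0.238, and 47%, 31%, 16% and 3% with SD 0.29.
- *Equal split at 0.025:* perfusion loses about 11, 8, 4 and under 1 points (SD 0.238). By the formula in step 1, power falls from 71.5% to 61.3%.
- *Both required:* joint power cannot exceed the stated 72%. With an assumed 80% for memory and independence it is 0.72 × 0.80 = 58%. The documents give no effect size or SD for memory.

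**5. An obvious repair that does not work well.** Suppose memory is tested only if the session F test on perfusion is significant and the average of the two levetiracetam sessions is below placebo. This is not a test of levetiracetam against placebo.

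- With SD 0.238, one dose lowering perfusion by 0.19 and the other raising it by 0.19, the levetiracetam average equals placebo. The condition is still met in about 50% of simulated trials.
- If only one dose works, adding the sign condition cuts power from 71% to 67% at r = 0.
- Its error rate stays within 5% when all three sessions are equal, but not under the wider null that the levetiracetam average equals placebo.

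**The case for a change.** The strongest case for a change is that it is cheap. A sentence naming free recall in the Behavioral Data paragraph, and another saying how the two outcomes will be judged, would need no new test, visit or subject. A pilot that declares two primary outcomes and an a priori main hypothesis could fairly be expected to say what counts as success.

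Much of this is factually right. Free recall is not repeated, no combining rule is stated, and neither primary analysis names its dose contrast. What does not stand is the consequence. Repeating free recall is a cross-reference within one document and alters no result. The combining rule is a choice among options with different costs, and the documents do not favour an either-counts reading. The Study Overview predicts lower hippocampal flow together with better memory, and section B1 puts the two outcomes under separate aims.

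Two side points are also true but small. Spatial memory appears in Aim 2, and working memory among the secondary outcomes, without a test assigned to either. Neither bears on a primary result, and the battery actually given is listed in full.

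**Conclusion.** No change is needed. The memory endpoint is defined once and is not contradicted, so analysts will use free recall and treat the other selective-reminding measures as supporting.

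The missing success rule is a gap of limited weight. The 8.5% to 9.8% error rate (4.3% to 5.0% in the predicted direction) rests on two assumptions outside the plan: 0.05 per test, and one positive outcome being enough. If both are required, or each aim is judged separately, there is no inflation. A formal hierarchy or split would buy strict control that a 20-subject mechanistic pilot does not need. Its price is the standing of the memory result or up to about 11 points of perfusion power, with the exact cost depending on a within-subject correlation that the documents do not give. Reporting both outcomes, each against its own aim, is a reasonable reading of the plan as it stands.

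### No visit (period) term is stated for the three-visit crossover analyses; any practice effect, most plausible for free recall, would stay in the error term and cost power

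*Combined protocol and SAP*

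**What the plan says.** The analysis models are in section B3, part B (Statistical Considerations), under Data Analysis.

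- **Imaging Data, hippocampal perfusion:** "we will use a repeated measures ANOVA with hippocampal perfusion and session (placebo, 2.5mg/kg and 7.5mg/kg) being the factors". Perfusion is the outcome, and the levels given for session are the three treatments, not visits 1 to 3.
- **Behavioral Data:** "Measures of memory encoding, retrieval and storage will be analyzed using repeated measures ANOVA". No factors are listed.
- **EEG Data:** "Measures will be analyzed using repeated measures ANOVA". No factors are listed.

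Order is dealt with in the design. Section B3.A.4 uses all six orders of the three treatments, with blocked randomization and counterbalancing; the block size is not given. On timing, B3.A.1 says "Each eligible subject will undergo three sessions, held 1-2 weeks apart", and the Study Plan (B3.A.6) has the same procedures at each of the three visits. On the memory outcome, B3.A.5 says "The primary endpoint for memory testing will be the free recall score from the Free and Cued Selective Reminding Test". On numbers, the Sample Size Justification says "We anticipate screening 25 subjects to enroll and randomize 20 eligible subjects".

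**The concern.** In a crossover each subject is measured at successive visits, so scores can drift with visit number whatever drug was given. Free recall is the obvious candidate: the same test is given three times at short intervals, and the documents mention neither alternate word lists nor a practice session. If visit is not in the model, this drift is counted as unexplained within-subject variation. The error mean square grows and real drug effects become harder to detect.

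With 20 subjects there is little power to spare. The plan states 72% for perfusion and gives no power figure for memory.

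**Working it through.** **The plan's own figure.** B2 gives atrophy-corrected hippocampal perfusion of 0.96 (SD 0.29) in AD and 0.77 (SD 0.17) in controls. The difference is 0.19 and the averaged SD is √[(0.29² + 0.17²)/2] = 0.2377. For two independent groups of 20, two-sided 5% (alpha and sidedness are not stated, so this is assumed), power = Φ(0.19/(0.2377 × √(2/20)) − 1.96) = Φ(0.568) = 71.5%. This matches the stated 72%. It is a between-group figure for perfusion only, so it serves here as a reference level.

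**Effect in within-subject units.** Assuming a within-subject correlation of 0.5 (none is given), within-subject SD = 0.29 × √(1 − 0.5) = 0.205, and 0.19/0.205 = 0.93 SD. With correlation 0 it would be 0.19/0.29 = 0.66 SD.

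**What an unmodelled visit effect does.** Let scores shift linearly by k within-subject SDs per visit. Around the subject's mean the shifts are −k, 0, +k, which adds 2k² to each subject's sum of squares, or 40k² over 20 subjects. With order nearly balanced, almost all of it falls into the residual, which has 38 df. The error mean square is therefore multiplied by about 1 + 40k²/38: 1.07 at k = 0.25, 1.26 at k = 0.5 and 2.05 at k = 1. If the shift occurs only from visit 1 to 2, the added sum is (2/3)k² per subject, and the factor at k = 0.5 is only 1 + 20 × (2/3) × 0.25/38 = 1.09.

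**Power by simulation.** n = 20, permuted blocks of six (assumed), both doses equally effective at 0.93 SD, two-sided 5%, subject-adjusted least squares, 40,000 replicates per setting. Entries are power without versus with a period term.

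| Shift per visit | Three-level F | Pooled doses v placebo |
|---|---|---|
| 0 | 83.5% v 83.2% | 90.8% v 90.6% |
| 0.25 SD, linear | 81.6% v 83.4% | 89.9% v 90.9% |
| 0.5 SD, linear | 75.0% v 83.7% | 86.1% v 90.8% |
| 1 SD, linear | 46.5% v 83.4% | 67.6% v 90.6% |

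If the 0.5 SD shift occurs only from visit 1 to 2, the pooled comparison goes from 90.7% to 89.2% (1.5 points). A separate run of the three-level F gives 84.2% to 81.5% (2.7 points).

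**Sensitivity to the drug effect.** No effect size for free recall is given. At k = 0.5 (linear), the pooled comparison gives 33.5% v 42.2% for an effect of 0.5 SD, 54.1% v 63.2% for 0.65 SD, and 71.2% v 78.9% for 0.78 SD. With the three-level F calibrated to 72% power when there is no shift (effect 0.808 SD), power is 69.4% v 71.8% at k = 0.25 and 60.8% v 71.7% at k = 0.5.

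**Type I error.** Without the term, the pooled test runs at 4.3%, 3.0% and 0.7% for k = 0.25, 0.5 and 1, against a nominal 5%.

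**Balance.** Twenty is three full sets of six orders plus two. With blocks of six and all subjects completing, the largest possible gap in mean visit number between two treatments is 0.15, or 0.075 SD at k = 0.5. With blocks of 12 the maximum is 0.30. If 2 of 20 are lost at random from blocks of six, the largest gap between treatments averages 0.16 visit. The worst case, 0.39, arises in 1.3% of such losses.

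**Cost of the term when there is no visit effect.** Exact noncentral t for the pooled comparison: 90.93% on 38 df and 90.85% on 36 df, a loss of about 0.1 point. The simulated loss is 0.2-0.3 points.

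**The case against.** The strongest reply is that order is already handled by counterbalancing, and that the evidence and the harm sit on different endpoints. The only model with listed factors is the one for perfusion, where a visit effect is less plausible: "Hippocampal perfusion is measured as a percentage of visual cortex perfusion", so both parts of the ratio come from the same scan. For free recall, where practice is plausible, the factors are simply not listed. The size of the loss rests on a visit effect that the documents do not quantify. A linear 0.5 SD per visit means a full SD by visit 3, whereas a gain confined to the second visit costs far less. This is also a pilot study, and the error is in the conservative direction.

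Most of that stands and limits the point. It does not remove it: counterbalancing balances the treatment means, but it does not take visit-to-visit variation out of the error term.

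A reader might also infer three stronger things that the documents do not support:

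- **That a period term is ruled out for memory and EEG.** It is only unstated there. The whole-brain imaging model is also loosely described ("measure changes after drug vs. placebo using a random effects model and accounting for the repeated measures design"). Even the perfusion sentence calls the outcome a factor, so it is weak evidence of a deliberately closed list.
- **That the dose comparisons are biased or false positives inflated.** With six orders and near balance, any residual bias is small, and type I error falls below 5%.
- **That a period term would deal with dropout.** The Data Safety Monitoring Plan (B8) ends participation for unexpected side effects or cognitive deterioration. Loss of the second kind may be related to the outcome, and a period term does not correct that.

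**Conclusion.** The point holds as a low-cost improvement to the analysis wording. No visit term is stated for a three-visit crossover, and if a visit effect exists its omission makes the tests conservative. At n = 20 and an assumed effect of 0.93 within-subject SD, the loss ranges from nil to 8-9 power points over linear shifts of 0 to 0.5 SD per visit, depending on the shape of the shift and the test used. At 1 SD it would be large, but that implies a 2 SD rise over three visits and should be read as an extreme.

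These sizes rest on assumed values for the visit shift, the within-subject correlation, the block size and, for free recall, the drug effect. The case is strongest for free recall, weaker for perfusion, and weakest for EEG, which has a pre-drug recording in every session.

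**What to change.** For free recall and hippocampal perfusion, replace the ANOVA wording with a mixed model: the outcome as dependent variable, treatment (placebo, 2.5 mg/kg, 7.5 mg/kg) and period (visit 1, 2, 3) as fixed effects, and subject as random effect. The same terms can be used for EEG, keeping the recording phase (before, during, after) as a factor or analysing change from that session's pre-drug recording; little gain is expected there.

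The cost is 2 of 38 error df, about 0.1-0.3 power points if there is no visit effect, and no new data. The term also adjusts for additive visit imbalance, whether from spreading 20 subjects over six orders or from random dropout. Stating it in advance avoids a choice made after a practice effect has been seen.
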